2.1 Aim

This study aimed to evaluate the effectiveness of virtual reality (VR) distraction in alleviating preoperative anxiety among patients scheduled for abdominal surgery

2.2 Design

This is a double-blinded (blinded to data collection and data analysis) randomized controlled trial conducted in accordance with the Consolidated Standards of Reporting Trials (CONSORT) guidelines. The study protocol is registered at ClinicalTrials.gov (ID: NCT05718661).

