3.1 Tools

Patient Information Form: Sociodemographic and clinical data.

Visual Analog Scale-Anxiety (VAS-A): Scores from 0 (no anxiety) to 10 (maximum anxiety).

Smart Bracelet (Xiaomi Mi Band 5): Measures heart rate variability-based stress (1100 scale).

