3.2 Procedures

Evaluation 1 (T1):

- Conducted in the patient's room in the morning.
- Informed consent obtained; forms and baseline anxiety/stress measurements completed.

Evaluation 2 (T2):

- Conducted 10–15 minutes after intervention or rest period

Virtual Reality Group:

- Watched a 2-hour 4K virtual forest video (<https://www.youtube.com/watch?v=uEMmpJgaXvo>).
- Used Zore G04E VR Shinecon headset with headphones and disposable eye covers.
- The researcher observed for any adverse effects.

Placebo-Video Group:

Watched the same video on a smartphone using disposable headphones

Control Group

No intervention; second evaluation conducted after ~15 minutes of rest.

4. Ethical Considerations

Approval was obtained from the Trakya University Ethics Committee (TÜTF-GOBAEK 2022/240) and the hospital administration (E-51088030-100-317619). All participants provided verbal and written informed consent. The study adhered to the Helsinki Declaration and CONSORT guidelines

5. Statistical Analysis Plan

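### Does naming only a VR-session observer in section 3.2 show that T2 data collection was not blinded?

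*Combined protocol and SAP*

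**What the plan says.** Section 2.2 makes the claim and defines it in the same sentence: "This is a double-blinded (blinded to data collection and data analysis) randomized controlled trial". The parenthesis limits the masking to those who collect and those who analyse the data. Patients are not included.

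Section 3.2 is the only account of conduct. For T2 it gives the timing, "Conducted 10–15 minutes after intervention or rest period", and names no collector. T1 is also described without saying who took it. The three arms read:

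- Virtual reality: "Used Zore G04E VR Shinecon headset with headphones and disposable eye covers", followed by "The researcher observed for any adverse effects".
- Placebo-video: "Watched the same video on a smartphone using disposable headphones".
- Control: "No intervention; second evaluation conducted after ~15 minutes of rest".

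Section 3.1 lists a 0 to 10 anxiety scale (VAS-A) and a smart-bracelet reading ("Measures heart rate variability-based stress"). Section 2.6 names the randomization tool but not who held the allocation. Section 5 lists software and tests, with no step that masks the analyst.

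**The concern.** The blinding claim comes without a mechanism. The only staff role in the procedures belongs to someone who sees the headset and so knows the arm. A reader can easily join these facts and conclude that the same person took T2 shortly afterwards, which would make the claim of blinded collection false for the VR arm.

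The observation line also appears under VR alone. Placebo-video patients saw the same film, so that contrast is the one that could isolate the headset. If only VR patients had a researcher beside them, the contrast would carry staff attention as well.

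The stake is interpretation. Patients could tell headset, phone and rest apart, and the VAS-A is presumably their own rating (inferred from the instrument, not stated). Masked collection would then limit prompting and recording bias, though not patient expectation. A reader who credits masking that did not happen would trust both VR contrasts too much.

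**Working it through.** The plan states no figure on this point, so the check is mainly one of reading.

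**Step 1: what a contradiction would need.** Two premises would have to be in the text.

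| Premise | What the text gives |
|---|---|
| The VR observer also collected T2 | Section 3.2 gives the researcher one task, safety observation. T1 and T2 are described with no collector named. |
| No staff were present in the placebo-video and control periods | Section 3.2 mentions no staff there. It does not say that nobody was present, and no section claims that attention was matched across arms. |

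Neither premise is stated. A separate person taking T2 without knowing the arm is consistent with sections 2.2, 2.6, 3.1, 3.2 and 5. The documents are silent here and do not conflict.

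**Step 2: the scope of the claim.** Because section 2.2 defines its own term, the fact that patients knew their exposure does not contradict it. With a headset, a phone and rest as the three conditions, patients would be expected to know.

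**Step 3: can the extent be counted?** Section 2.5 plans 96 patients, 32 per arm, so each VR contrast has 32 + 32 = 64 T2 assessments. The unmasked share depends on facts the documents do not give:

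- A separate masked collector: 0 of 64.
- The observer takes T2 for VR patients only, and a masked person takes the rest: 32 of 64.
- One researcher watches every VR session and takes T2 in all arms. That person knows any patient they did not watch was not in VR, so VR versus non-VR is known for 64 of 64.

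The text supports no choice among these.

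**Step 4: can the bias be sized?** The nearest calculation is a margin. Assume three pairwise tests under the Bonferroni rule in section 5.4, two-sided, so alpha = 0.05/3 = 0.0167. With 62 degrees of freedom the critical t is 2.4607. The smallest significant difference is 2.4607 × √(2/32) = 2.4607 × 0.25 = 0.615 SD. Against the planning value in section 2.5 the margin is 0.920 − 0.615 = 0.305 SD. This is only the distance from a planning assumption to a critical value. It would be the same for any source of bias, so it says nothing about masking.

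**Step 5: would the analysis change?** Naming the collector and describing how collector and analyst were masked would alter no outcome, test or comparison in section 5.4. A masked analyst could run every listed test on coded group labels.

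**The case for a change.** The strongest case for acting is that both halves of the claim, collection and analysis, are asserted with no means given, in a document that says the trial followed CONSORT. The anxiety outcome is a rating taken soon after exposures that patients could plainly distinguish, so masked collection is one of the few protections available. Asking who was masked, and how, is cheap. Data collection ended in December 2024, so only wording and a look at the records would be needed.

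Much of this stands. The gap is genuine, and a sentence or two in the report would close it: who took T2, how that person and the analyst were kept unaware of the arm, and whether staff were present in the placebo-video and control periods. Two conditional consequences also stand. If the records showed that the VR observer took T2, the claim of blinded collection could not be kept. If staff attended VR sessions only, VR versus placebo-video would have to be read as headset plus attention.

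Both consequences depend on facts outside the documents. The objection does not show that either condition held. Nor does it justify dropping the term double-blinded whatever the records say: section 2.2 defines it, and it would be true as defined if collector and analyst were masked.

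**Conclusion.** No change to the plan follows. Sections 3.2 and 5 leave out how the blinding in section 2.2 was achieved. That is a reporting gap and does not show unblinding or unequal attention. It can be filled from the study records when the trial is reported.

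This rests on one assumption, that the trial ran as section 2.2 states, with collector and analyst both masked. On that footing the results and conclusions are unaffected. The documents neither confirm nor contradict the assumption. They allow 0, 32 or 64 unmasked T2 assessments out of 64 in each VR contrast, and they support no estimate of bias.

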2.3 Study Setting and Period

The study was conducted between December 1, 2022, and December 20, 2024, at the General Surgery Service of a university hospital in the Trakya region, Edirne, Türkiye. The hospital serves as a referral center and contributes to medical and health sciences education.

2.4 Participants

Inclusion Criteria:

- Adults aged ≥ 18 years
- Undergoing elective abdominal surgery (e.g., appendectomy, hernia, gallbladder/pancreas surgery)
- Awaiting transfer to the operating room in the morning
- Able to communicate and provide informed consent

Exclusion Criteria:

- Abdominal cancer surgery
- Emergency or unplanned surgery
- Isolation status
- Visual/auditory impairments
- Neurological disorders (e.g., vertigo)

2.5 Sample Size

The sample size was calculated based on the study by Mosso et al. (2009) using G*Power 3.1.9.7 software. With an effect size of $d=0.920$, $\alpha=0.05$, and $\text{power}=0.95$, a total of 96 patients were required (32 in each group).

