2.6 Randomization

Patients were randomized using the Research Randomizer tool (<https://www.randomizer.org/>) into three groups: VR, placebo-video, and control.

3. Interventions and Data Collection

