5.1. Software

Data analysis was performed using IBM SPSS Statistics for Windows, Version 28.0

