5.2. Descriptive Statistics

- Continuous variables (e.g., age, anxiety, stress): Mean, SD, median, min, max
- Categorical variables (e.g., gender, education, chronic diseases): Frequency and percentage

5.3.Normality Testing

Shapiro-Wilk test for all continuous variables

5.4.Inferential Statistics:

-Between-Group Comparisons:

Kruskal-Wallis H Test for comparing continuous variables across the three groups

Mann-Whitney U Test with Bonferroni correction for post-hoc pairwise comparisons

-Within-Group Comparisons (T1 vs. T2):

Wilcoxon Signed Ranks Test

-Categorical Variables:

Pearson Chi-Square Test

5.5.Statistical Significance

Significance level set at $p < 0.05$

Confidence interval: 95%

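### The 95% power in section 2.5 does not carry the Bonferroni correction of section 5.4: a single corrected pair with true d = 0.92 has about 87% (two-sided, three pairs, normal data)

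*Combined protocol and SAP*

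**What the plan says.** Section 2.5 (Sample Size) bases the calculation on one earlier study. It enters d = 0.920, alpha 0.05 and power 0.95 in G*Power, and states that "a total of 96 patients were required (32 in each group)". It does not say which test, contrast, endpoint or sidedness was used, and it mentions no adjustment for multiplicity.

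Section 2.6 (Randomization) allocates patients "into three groups: VR, placebo-video, and control", so there are three possible pairs.

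Section 5.4 (Inferential Statistics) plans a "Kruskal-Wallis H Test for comparing continuous variables across the three groups", then a "Mann-Whitney U Test with Bonferroni correction for post-hoc pairwise comparisons". It gives neither the Bonferroni divisor nor the sidedness. Section 5.5 sets the significance level at 0.05.

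**The concern.** Cohen's d describes a difference between two groups, and the alpha in section 2.5 is the full 0.05. The pairwise tests in section 5.4 are run at a smaller alpha, so a sample size found at 0.05 cannot give the same power there.

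This matters because Kruskal-Wallis does not show which group differs. Any statement that VR beats the placebo video or the control rests on the corrected pairs. A reader who takes 95% as the power of those pairs will read too much into a non-significant one. The risk is greatest for VR against video, because the true difference there is smaller if the video itself has some effect.

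**Working it through.** **Inputs.** From section 2.5: d = 0.92, alpha = 0.05, power 0.95, n = 32 per group. From section 2.6: three groups, hence 3 pairs. From section 5.4: Mann-Whitney with Bonferroni. Assumed, because the plan does not say: two-sided tests, divisor 3 and normal data. Alternatives are shown below.

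**Step 1: reproduce the plan's figure.** For a two-group t-test, the noncentrality is d × √(n/2) with 2n − 2 degrees of freedom.
- n = 32: 0.92 × √16 = 3.68, 62 df, two-sided power at 0.05 = 0.952.
- n = 31: 0.92 × √15.5 = 3.62, 60 df, power = 0.946.

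So 32 is the exact minimum for 95%. A one-sided test at 0.05 would need 27. A three-group ANOVA gives a total of 87 if video equals control and 114 if video is midway between control and VR. It gives 96 if video sits about 10–12% of the way from control to VR, a pattern the plan does not state. The unadjusted two-sided t-test is therefore the likely basis, but it is inferred.

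**Step 2: power of a planned pair.** For normal data the Mann-Whitney test has asymptotic relative efficiency (ARE) 3/π, so the effective n is 32 × 3/π = 30.56 and the noncentrality is 0.92 × √(30.56/2) = 3.60. Corrected alpha is 0.05/3 = 0.0167.

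| Mann-Whitney, n = 32 per group, d = 0.92, normal data | Power |
|---|---|
| Two-sided, 0.05 (no correction) | 0.943 |
| Two-sided, 0.05/2 | 0.899 |
| Two-sided, 0.05/3 | 0.867 |
| One-sided, 0.05/3 | 0.919 |

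Simulation at two-sided 0.05/3 (100,000 trials) gives 0.864. Requiring a significant Kruskal-Wallis test first leaves 0.862–0.866, depending on where the third group lies. The shortfall from 0.952 is 0.085. Of this, 0.009 comes from using ranks (0.952 to 0.943) and 0.076 from the correction (0.943 to 0.867).

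**Step 3: effect size for 95%.** With 32 per group, a two-sided Mann-Whitney pair reaches 95% at d = 1.059 with divisor 3, or 1.016 with divisor 2.

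**Step 4: distributions other than the normal.** Two-sided, divisor 3, d = 0.92:
- Minimum ARE (0.864): 0.825
- Uniform: 0.820
- Logistic: 0.902
- Laplace: 0.948
- Exponential: 0.979

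The anxiety scale in section 3.1 has "Scores from 0 (no anxiety) to 10 (maximum anxiety)". Simulated as whole scores clipped to that range, with d fixed at 0.92 after clipping, power is 0.858–0.889 (0.893–0.916 with divisor 2). This assumes a latent SD of 2–3 and a control mean of 3–7, neither of which the plan gives. These figures are illustrations, not bounds.

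**Step 5: all three arms together.** The three pairs cannot all have d = 0.92. With VR–control at 0.92 and normal data (simulated, pairs at two-sided 0.05/3):

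| Video's position from control to VR | Kruskal-Wallis | VR–control | VR–video | At least one VR pair |
|---|---|---|---|---|
| 0% | 0.962 | 0.866 | 0.864 | 0.949 |
| 10% | 0.945 | 0.864 | 0.773 | 0.929 |
| 25% | 0.918 | 0.865 | 0.585 | 0.900 |
| 50% | 0.894 | 0.864 | 0.258 | 0.871 |

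**The case against.** **The basis is unstated, and one reading already carries the correction.** A one-sided test at 0.05/2, correcting only for the two VR contrasts, has virtually the same power as a two-sided test at 0.05. It also gives 32 per group, with Mann-Whitney power 0.943, and the aim in section 2.1 is directional. Reproducing 32 therefore does not prove that the correction was left out. This stands as a possibility and is why the G*Power output must be checked first. It is not the better reading: section 2.5 gives alpha as 0.05 with no adjustment, and nothing in the plan mentions one-sided tests or limits the pairs to two.

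**The 95% may describe the global test.** It roughly holds for Kruskal-Wallis (0.96) and for at least one VR contrast (0.95) if video equals control, and the plan calls the pairs post hoc. But both figures fall if video has an effect (0.89 and 0.87 midway), and the plan never says that 95% is global power.

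**The low VR–video power is mostly not a Bonferroni effect.** This is right. With video midway, the uncorrected Mann-Whitney power is already about 0.42, against 0.26 corrected; at 25% it is 0.76 against 0.59. Those figures show how far 95% can mislead for that pair, not what the correction alone costs.

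**87% depends on normality.** It does. Laplace data reach about 95% and exponential data exceed it, while uniform data fall to 82%. The bracelet stress score was not simulated.

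**The consequence is small.** Agreed. The study is complete, and the sample size is reproduced rather than miscalculated.

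**Conclusion.** The concern holds, as a minor one. On the best-supported reading of section 2.5, an unadjusted two-sided t-test, the 95% is not the power of the corrected pairwise tests in section 5.4. For one pair with true d = 0.92 that power is about 87%, roughly 8 percentage points lower, and nearly all of the gap is the Bonferroni step. The figure assumes two-sided tests, divisor 3 and normal data; divisor 2 gives about 90%, and one-sided testing with divisor 3 gives about 92%. Type I error is not affected. The arithmetic is firm, but the basis of the original calculation remains an inference until the sponsor confirms it.

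**What to change.** 1. Retrieve the G*Power output and confirm the test, contrast, endpoint and sidedness.
2. If it shows the unadjusted t-test, restate section 2.5, for example: *32 per group gives 95% power for an unadjusted two-sided two-group t-test at d = 0.92. A single two-sided Mann-Whitney comparison with true d = 0.92, Bonferroni-corrected for three pairs (alpha = 0.0167), has about 87% power assuming normal data, and reaches 95% at d of about 1.06. Pairs with a smaller true difference, such as VR against video if video has some effect, have less.* If the divisor used was 2, give about 90% and d of about 1.02. If the output shows another basis, including a one-sided corrected one, report that instead.
3. In section 5.4, state the divisor and sidedness actually used, and keep Bonferroni.
4. Section 5.1 reports that "Data analysis was performed using IBM SPSS Statistics for Windows, Version 28.0", so mark both edits as clarifications made after analysis.

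The cost is a file lookup, wording in two sections and a less favourable stated power. No patients are added, and neither the tests nor the multiplicity rule changes.

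### The power of 0.95 in section 2.5 belongs to one unnamed two-group t-test at 0.05, not to the three-arm analysis planned in section 5.4

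*Combined protocol and SAP*

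**What the plan says.** Section 2.5 rests the sample size on one earlier study ("The sample size was calculated based on the study by" a cited 2009 report). It gives d=0.920, alpha 0.05 and power 0.95, and ends with "a total of 96 patients were required (32 in each group"). It does not say which arms, which endpoint (VAS-A or bracelet stress), which test or how many sides the calculation used.

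Section 2.6 randomises "into three groups: VR, placebo-video, and control". In section 3.2 the VR arm watches a forest video through a headset. The placebo-video arm "Watched the same video on a smartphone using disposable headphones". For the control arm the entry is "No intervention; second evaluation conducted after ~15 minutes of rest".

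Section 5.4 compares groups with a "Kruskal-Wallis H Test for comparing continuous variables across the three groups", followed by a "Mann-Whitney U Test with Bonferroni correction for post-hoc pairwise comparisons". Section 5.5 sets significance at p < 0.05 and confidence intervals at 95%. No second effect size or power appears anywhere.

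**The concern.** Cohen's d describes one difference between two groups. This trial has three arms, three pairwise differences and a global test. A single d with a single power can describe only one of these, and section 2.5 does not say which one. The alpha used for sizing is also not the level at which the pairwise tests will be judged.

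What is at stake is how a null result is read. Both video arms see the same film, so VR versus placebo-video is the comparison that shows what the headset adds. A reader who takes the 0.95 in section 2.5 as the power of that comparison would treat a non-significant result as strong evidence of no difference. The power could be much lower than that.

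**Working it through.** **Inputs.** From section 2.5: d=0.920, alpha 0.05, power 0.95, n=32 per group. From sections 2.6 and 5.4: three arms, hence three pairs, and Bonferroni gives 0.05/3 = 0.0167 per pair. Assumed here: normal data, common SD, two-sided tests.

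**1. Reproducing the plan's figure.** For a two-sample t-test the noncentrality is d × √(n/2) = 0.92 × √16 = 3.68, with 2 × 32 − 2 = 62 degrees of freedom. At two-sided 0.05 the critical value is 1.999 and the noncentral t gives power 0.952. With n=31 the power is 0.946, so 32 is the smallest n that reaches 0.95. The other calculations tried do not give 32:

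- one-sided t-test: 27 per group
- Mann-Whitney (relative efficiency 0.955): 34
- t-test at 0.0167: 41
- one-way ANOVA with a range of 0.92 SD: 29 if the middle arm equals an end arm, 38 if it lies halfway. A middle mean chosen between these would give 32, but section 2.5 states none.

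The stated number is therefore a two-group calculation whose per-group n was applied to three arms: 3 × 32 = 96.

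**2. Power of the planned pairwise test at d=0.92.** At 0.0167 the critical value rises to 2.461. With the same noncentrality of 3.68, power is 0.885 (t-test). For Mann-Whitney, using an effective n of 32 × 0.955, it is 0.867. So the power is about 87 to 88%, against 95% stated.

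**3. Power of the global test.** Set the arm means at 0, x and 0.92 SD with 32 per arm. The Kruskal-Wallis figures come from 8,000 simulated trials each.

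| Middle arm x | ANOVA | Kruskal-Wallis |
|---|---|---|
| 0 | 0.971 | 0.961 |
| 0.23 | 0.932 | 0.916 |
| 0.46 | 0.910 | 0.891 |
| 0.69 | 0.932 | 0.921 |

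The global test reaches 0.95 when the middle arm coincides with an end arm, and falls to about 0.89 when it lies halfway.

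**4. VR versus placebo-video, if d=0.92 means VR versus control.** The differences must add up: (VR − video) + (video − control) = (VR − control). If the phone video alone gives a share s of the effect, VR versus placebo-video is 0.92 × (1 − s). The share is not in the documents, so a range is shown (t-test, n=32 per arm).

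| Share s | d, VR versus placebo-video | Power at 0.05 | Power at 0.0167 |
|---|---|---|---|
| 0% | 0.92 | 95% | 88% |
| 25% | 0.69 | 78% | 62% |
| 50% | 0.46 | 44% | 28% |
| 75% | 0.23 | 15% | 7% |

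**5. Detectable difference.** With 32 per arm, 80% power is reached at 0.83 SD at 0.0167 and at 0.71 SD at unadjusted 0.05 (t-test).

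**The case against.** The best defence is that nothing in section 2.5 is miscalculated. The 32 reproduces exactly, and a design d is a target: 32 per arm detects a 0.92 SD difference in any one pair with 95% power at 0.05. This stands, and it rules out several stronger readings.

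- A reader might infer that section 2.5 claims all three true differences are 0.92, which the addition rule forbids. The section makes no such claim.
- A reader might infer that the three contrasts cannot all have 95% power. If neighbouring arms differed by 0.92 SD and VR and control by 1.84 SD, every pair would reach it at unadjusted 0.05. Nothing in the documents supports so large an effect, but it is not impossible.
- A reader might infer that VR versus placebo-video has 95% power only if the video is inert. That requires d to mean VR versus control. If d was meant for VR versus placebo-video, that contrast has its 95% at 0.05 whatever the video does.
- A reader might take 44% or 28% as the power of the trial. These are scenario values. The documents give no ground for a share of one half, and none for zero.

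It can also be said that the pairwise tests are labelled post-hoc, that the global test stays fairly close to 0.95, and that section 2.1 does not name VR versus placebo-video as the main contrast. Those points limit the consequence. They do not make 0.95 the power of the planned tests: on any reading of d, the pairwise tests are judged at a stricter level than the one used for sizing.

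**Conclusion.** The point holds as a mismatch between the stated power and the planned analysis, together with an unnamed contrast. It is not an arithmetic error. For each pairwise test at d=0.92, the shortfall is about 7 to 8 percentage points (95% stated, about 87 to 88% under the plan). For the global test it ranges from none to about 6 points. These figures rest on normal data, a common SD and all 96 patients analysed. With other distributions the Mann-Whitney figure could move either way.

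The much lower figures for VR versus placebo-video are conditional on d being VR versus control and on the video having some effect of its own. They show why the contrast must be named. They do not establish that this comparison is underpowered.

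**What to change.** In section 2.5:

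- State which pair of arms, which endpoint and which test d=0.920 and power 0.95 came from. The sponsor should confirm this from the original calculation. Since section 2.3 puts the end of the study in December 2024, a contrast should not be assigned afterwards; if it cannot be recovered, say so.
- Say that 0.95 is the power of a two-group, two-sided t-test at unadjusted 0.05, and that the planned Bonferroni-corrected pairwise tests have about 87 to 88% power at d=0.92.
- Add that 32 per arm give 80% power for about 0.83 SD at 0.0167 (0.71 SD unadjusted). If d is confirmed as VR versus control, show the power range for VR versus placebo-video by assumed video share, labelled as an assumption.

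In section 5.4, add one sentence: a non-significant VR versus placebo-video result is reported with the 95% confidence interval for the difference and is not presented as evidence of equal effect. This is ordinary good reporting.

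The cost is a short paragraph and a less favourable stated power. No patients are added and no test changes.
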